## 12.8.1 Primary endpoint

Not applicable.

### 12.8.2 Secondary endpoints

Not applicable.

# 13 Ethical considerations and administrative procedures

# 13.1 Regulatory and ethical compliance

This clinical study was designed and shall be implemented, executed and reported in accordance with the ICH Harmonized Tripartite Guidelines for Good Clinical Practice, with applicable local regulations (including European Directive 2001/20/EC, US CFR 21), and with the ethical principles laid down in the Declaration of Helsinki.

# 13.2 Responsibilities of the investigator and IRB/IEC

Before initiating a trial, the investigator/institution must obtain approval/favorable opinion from the Institutional Review Board/Independent Ethics Committee (IRB/IEC) for the trial protocol, written informed consent form, consent form updates, participant recruitment procedures (e.g., advertisements) and any other written information to be provided to participants. Prior to study start, the investigator is required to sign a protocol signature page confirming his/her agreement to conduct the study in accordance with these documents and all of the instructions and procedures found in this protocol and to give access to all relevant data and records to Novartis monitors, auditors, Novartis Quality Assurance representatives, designated agents of Novartis, IRBs/IECs, and regulatory authorities as required. If an inspection of the clinical site is requested by a regulatory authority, the investigator must inform Novartis immediately that this request has been made.

# 13.3 Publication of study protocol and results

The protocol will be registered in a publicly accessible database such as clinicaltrials.gov and as required in EudraCT. In addition, after study completion (defined as last patient last visit) and finalization of the study report the results of this trial will be submitted for publication and posted in a publicly accessible database of clinical trial results, such as the Novartis clinical trial results website and all required Health Authority websites (e.g., Clinicaltrials.gov, EudraCT etc.).

For details on the Novartis publication policy including authorship criteria, please refer to the Novartis publication policy training materials that were provided to you at the trial investigator meetings.

# 13.4 Quality Control and Quality Assurance

Novartis maintains a robust Quality Management System (QMS) that includes all activities involved in quality assurance and quality control, to ensure compliance with written Standard Operating Procedures as well as applicable global/local GCP regulations and ICH Guidelines.

Audits of investigator sites, vendors, and Novartis systems are performed by auditors, independent from those involved in conducting, monitoring or performing quality control of the clinical trial. The clinical audit process uses a knowledge/risk-based approach.

Audits are conducted to assess GCP compliance with global and local regulatory requirements, protocols and internal Standard Operating Procedures, and are performed according to written Novartis processes.

## 13.5 Participant Engagement

The following participant engagement initiatives are included in this study and will be provided, as available, for distribution to study participants at the timepoints indicated. If compliance is impacted by cultural norms or local laws and regulations, sites may discuss modifications to these requirements with Novartis.

- Thank You letter
- Plain language trial summary after CSR publication
- Individual study results after CSR publication
- Trial Feedback Questionnaires 3 timepoints: at the start, during and at the end of the trial.

#### 14 Protocol adherence

This protocol defines the study objectives, the study procedures and the data to be collected on study participants. Additional assessments required to ensure safety of participants should be administered as deemed necessary on a case by case basis. Under no circumstances including incidental collection is an investigator allowed to collect additional data or conduct any additional procedures for any purpose involving any investigational drugs under the protocol, other than the purpose of the study. If despite this interdiction prohibition, data, information, observation would be incidentally collected, the investigator shall immediately disclose it to Novartis and not use it for any purpose other than the study, except for the appropriate monitoring on study participants.

Investigators ascertain they will apply due diligence to avoid protocol deviations. If an investigator feels a protocol deviation would improve the conduct of the study this must be considered a protocol amendment, and unless such an amendment is agreed upon by Novartis and approved by the IRB/IEC and Health Authorities, where required, it cannot be implemented.

#### 14.1 Protocol amendments

Any change or addition to the protocol can only be made in a written protocol amendment that must be approved by Novartis, health authorities where required, and the IRB/IEC prior to implementation.

Notwithstanding the need for approval of formal protocol amendments, the investigator is expected to take any immediate action required for the safety of any participant included in this study, even if this action represents a deviation from the protocol. In such cases, Novartis should be notified of this action and the IRB/IEC at the study site should be informed according to local regulations.

#### 16 **Appendices**

#### 16.1 Appendix 1: Clinically notable laboratory values and vital signs

The following specific criteria have been identified for this study. Should these criteria be met, a re-test must be done within 5 days after the first assessment. Discontinuation of the study treatment should be considered if the abnormal hematology parameter is confirmed:

- Hemoglobin: < 10 g/dl
- Platelets: < 75 000/mm3
- Leukocytes: < 3 000/mm3
- Neutrophils: < 1 500/mm3

For all other laboratory assessments, the central laboratory will flag laboratory values falling outside of the normal ranges on the central laboratory report (which the investigator should review and sign-off) and the investigator will report any values considered clinically significant in the eCRF.

Refer to Section 16.2 for clinically notable laboratory values for hepatotoxicity.

Refer to Section 16.3 for clinically notable laboratory values for nephrotoxicity.

Notable values for vital signs and change from baseline will be summarized.

Notable values are defined as follows:

- heart rate of < 50 or > 100 bpm
- systolic blood pressure of < 90 and  $\ge 140$  mmHg
- diastolic blood pressure of < 60 and  $\ge 90$  mmHg.

For ECGs, a notable QTc value is defined as an absolute QTc (Fridericia's) interval of greater than 450 ms for males or greater than 460 ms for females QTcF increase of ≥60 ms compared to baseline QTcF value – all such ECGs will be flagged by the central CRO's cardiologist and require assessment for clinical relevance by the investigator.

## Appendix 2: Liver event and laboratory trigger definitions & 16.2 follow-up requirements

**Table 16-1** Liver event and laboratory trigger definitions

Novartis

able 10-1 Livel event and laboratory trigger definitions		
	Definition/ threshold	
Liver laboratory triggers	ALT or AST > 5 × ULN	
If ALT, AST and total bilirubin normal at baseline:	
 
ALP > 2 × ULN (in the absence of known bone pathology)
 
	
	
 
Total bilirubin > 3 × ULN (in the absence of known Gilbert syndrome)
 
	
	
 
ALT or AST > 3 × ULN and INR > 1.5
 
	
	
 
Potential Hy's Law cases (defined as ALT or AST > 3 × ULN and Total bilirubin > 2 × ULN [mainly conjugated fraction] without notable increase in ALP to > 2 × ULN)
 
	
	
 
Any clinical event of jaundice (or equivalent term)
 
	
	
 
ALT or AST > 3 × ULN accompanied by (general) malaise, fatigue, abdominal pain, nausea, or vomiting, or rash with eosinophilia
 
	
	
 
Any adverse event potentially indicative of a liver toxicity
 
	

ALP: Alkaline phosphatase, ALT: Alanine aminotransferase, AST: Aspartate aminotransferase, ULN: upper limit of normal

Follow up requirements for liver laboratory triggers: ALT, AST and **Table 16-2** TBL

		Action Taken		
Trigger	Liver Symptoms	Monitoring	Follow-up Monitoring	Study Medication
ALT				
ALT > 3 ULN TBL normal, or no change for participants with Gilbert's syndrome	None	Measure ALT, AST, ALP, GGT, TBL, INR, albumin, CK, and GLDH in 48-72 hours	Follow up for symptoms	Continue dosing
ALT > 5 x ULN for more than two weeks TBL normal, or no change for participants with Gilbert's syndrome	None	Measure ALT, AST, ALP, GGT, TBL, INR, albumin, CK, and GLDH in 48-72 hours	Follow-up for symptoms Initiate close monitoring and workup for competing etiologies	Interrupt Study drug can be restarted only if another etiology is identified and liver enzymes return to baseline
ALT > 8 x ULN TBL normal, or no change for participants with Gilbert's syndrome	None	Measure ALT, AST, ALP, GGT, TBL, INR, albumin, CK, and GLDH in 48-72 hours	Follow-up for symptoms Initiate close monitoring and workup for competing etiologies	Interrupt Study drug can be restarted only if another etiology is identified and liver enzymes return to baseline
ALT > 3 x ULN TBL > 2 x ULN (or INR > 1.5) For patients with	None	Measure ALT, AST, ALP, GGT, TBL, INR, albumin, CK,	Follow-up for symptoms Initiate close monitoring and	Interrupt Study drug can be restarted only if another etiology is

		Action Taken		
Trigger	Liver Symptoms	Monitoring	Follow-up Monitoring	Study Medication
Gilbert's syndrome: Doubling of direct bilirubin		and GLDH in 48-72 hours	workup for competing etiologies	identified and liver enzymes return to baseline
ALT > 3 x ULN TBL normal or elevated	Severe fatigue, nausea, vomiting, right upper quadrant pain	Measure ALT, AST, ALP, GGT, TBL, INR, albumin, CK, and GLDH in 48-72 hours	Follow-up for symptoms Initiate close monitoring and workup for competing etiologies	Interrupt Study drug can be restarted only if another etiology is identified and liver enzymes return to baseline
Total Bilirubin (isola	ated)			
>1.5 – 3.0 ULN		Repeat LFTs within 48-72 hours	Monitor LFTs weekly until resolution¹ to ≤ Grade 1 or to baseline	Continue dosing
> 3 - 10 × ULN (in the absence of known Gilbert syndrome)		Repeat LFT within 48-72 hours Hospitalize if clinically appropriate Establish causality Record the AE and contributing factors (e.g., conmeds, med hx, lab) in the appropriate CRF	Monitor LFTs weekly until resolution¹ to ≤ Grade 1 or to baseline (ALT, AST, total bilirubin, Alb, PT/INR, ALP and GGT) Test for hemolysis (e.g., reticulocytes, haptoglobin, unconjugated [indirect] bilirubin)	Interrupt
> 10 x ULN		Hospitalize the participant Establish causality Record the AE and contributing factors(e.g., conmeds, med hx, lab) in the appropriate CRF	ALT, AST, total bilirubin, Alb, PT/INR, ALP and GGT until resolution  (frequen cy at investigator discretion)	Discontinue treatment immediately
General Clinical Syr	mptoms			
Any AE potentially inc toxicity including: (Ge fatigue, abdominal pa vomiting, or rash with	eneral) malaise, ain, nausea, or	Establish causality Record the AE and contributing factors(e.g., conmeds, med hx, lab) in the appropriate CRF	Investigator discretion	Consider study treatment interruption or discontinuation

<sup>1Resolution is defined as an outcome of one of the following: (1) return to baseline values, (2) stable values at three subsequent monitoring visits at least 2 weeks apart, (3) remain at elevated level after a maximum of 6 months, (4) liver transplantation, and (5) death

Alb: Albumin, ALP: Alkaline phosphatase, ALT: Alanine aminotransferase, AST: Aspartate aminotransferase, CK: Creatinine kinase, CRF: Case report form, GGT: Gamma-glutamyl transferase, GLDH: glutamate dehydrogenase, INR: International Normalized Ratio, LFTs: Liver function tests, Med Hx: medical history, PT: Prothrombin time, TBL: Total bilirubin, ULN: upper limit of normal

Criteria	Actions required	Follow-up monitoring
Total Bilirubin (isolated)	·	
>1.5 - 3.0 ULN	- Maintain treatment- Repeat LFTs within 48-72 hours	Monitor LFTs weekly until resolution to ≤ Grade 1 (≤ 1.5 ULN) or to baseline
> 3 - 10 x ULN (in the absence of known Gilbert syndrome)	
 
Interrupt treatment
 
Repeat LFT within 48-72 hours
 
Hospitalize if clinically appropriate
 
Establish causality
 
Record the AE and contributing factors(e.g., conmeds, med hx, lab) in the appropriate CRF
 
	- Monitor LFTs weekly until resolution to ≤ Grade 1 (≤ 1.5 ULN) or to baseline (ALT, AST, total bilirubin, Alb, PT/INR, ALP and GGT) - Test for hemolysis (e.g., reticulocytes, haptoglobin, unconjugated [indirect] bilirubin)
> 10 x ULN	
 
Discontinue the study treatment immediately
 
Hospitalize the participant
 
Establish causality
 
Record the AE and contributing factors(e.g., conmeds, med hx, lab)in the appropriate CRF
 
	ALT, AST, total bilirubin, Alb, PT/INR, ALP and GGT until resolution (frequency at investigator discretion)
Any AE potentially indicative of a liver toxicity	
 
Consider study treatment interruption or discontinuation
 
Hospitalization if clinically appropriate- Establish causality- Record the AE and contributing factors (e.g., conmeds, med hx, lab) in the appropriate CRF
 
	Investigator discretion

Based on investigator's discretion investigation(s) for contributing factors for the liver event can include: Serology tests, imaging and pathology assessments, hepatologist's consultancy; obtaining more detailed history of symptoms and prior or concurrent diseases, history of concomitant drug use, exclusion of underlying liver disease.

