- 14. Evidence of clinically significant cardiovascular (such as but not limited to myocardial infarction, unstable ischemic heart disease, NYHA Class III/IV left ventricular failure, arrhythmia and uncontrolled hypertension within 12 months prior to Visit 1), neurological, psychiatric, pulmonary, renal, hepatic, endocrine, metabolic, hematological disorders, gastrointestinal disease or immunodeficiency that, in the investigator's opinion, would compromise the safety of the participant, interfere with the interpretation of the study results or otherwise preclude participation or protocol adherence of the participant
- 15. Uncontrolled disease states, such as asthma, or inflammatory bowel disease, where flares are commonly treated with oral or parenteral corticosteroids
- 16. Hematology parameters at screening:
  - Hemoglobin: < 10 g/dL
  - Platelets: < 100 000/mm^3
  - Leucocytes: <3 000/mm^3
  - Neutrophils: < 1 500/mm^3
- 17. Significant bleeding risk or coagulation disorders
- 18a. History of gastrointestinal bleeding, e.g., in association with use of nonsteroidal antiinflammatory drugs (NSAIDs), that was clinically relevant (e.g., for which intervention was indicated or requiring hospitalization or blood transfusion)
- 19a. Requirement for anti-platelet medication, except for acetylsalicylic acid up to 100 mg/d or clopidogrel up to 75 mg/d. The use of dual anti-platelet therapy (e.g., acetylsalicylic acid + clopidogrel) is prohibited.
- 20. Requirement for anticoagulant medication (e.g., warfarin or Novel Oral Anti-Coagulants (NOAC))
- 21. History or current hepatic disease including but not limited to acute or chronic hepatitis, cirrhosis or hepatic failure or Aspartate Aminotransferase (AST)/ Alanine Aminotransferase (ALT) levels of more than 1.5 x upper limit of normal (ULN) or International Normalized Ratio (INR) of more than 1.5 at screening
- 22. History of renal disease, creatinine level above 1.5x ULN, or estimated Glomerular Filtration Rate (eGFR) <45 ml/min (using the Cockcroft-Gault equation) at screening
- 23. Evidence of an ongoing Hepatitis C infection (e.g., defined by the detection of hepatitis C-ribonucleic acid (HCV-RNA) at screening) and/or an ongoing Hepatitis B infection (defined by the detection of Hepatitis B virus surface antigen (HBsAg) and/or hepatitis B virus (HBV)-DNA at screening; participants who are positive for anti-hepatitis B core

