# 10.2 Additional Safety Monitoring

## 10.2.1 Liver safety monitoring

To ensure participant safety and enhance reliability in determining the hepatotoxic potential of an investigational drug, a standardized process for identification, monitoring and evaluation of liver events has to be followed.

Please refer to Table 16-1 in Section 16.2 for complete definitions of liver laboratory triggers.

Once a participant is exposed to study treatment, every liver event defined in Table 16-1 should be followed up by the investigator or designated personnel at the trial site, as summarized below. Additional details on actions required in case of liver events are outlined in Table 16-2 and Table 16-3. Repeat liver chemistry tests (i.e., ALT, AST, TBL, PT/INR, ALP and GGT) to confirm elevation.

These liver chemistry repeats will be performed using the central laboratory. If results will not be available from the central laboratory, then the repeats can also be performed at a local laboratory to monitor the safety of the participant. If a liver event is subsequently reported, any local liver chemistry tests previously conducted that are associated with this event should have results recorded on the appropriate CRF.

- If the initial elevation is confirmed, close observation of the participant will be initiated, including consideration of treatment interruption if deemed appropriate.
- Discontinuation of the investigational drug (refer to Section 9.1 and Section 16.2), if appropriate
- Hospitalization of the participant if appropriate
- Causality assessment of the liver event
- Thorough follow-up of the liver event should include, based on investigator's discretion:
  - serology tests, imaging and pathology assessments, hepatologist's consultancy; obtaining more detailed history of symptoms and prior or concurrent diseases, history of concomitant drug use, exclusion of underlying liver disease

All follow-up information and procedures performed must be recorded as appropriate in the CRF.

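### Table 16-1 limits its liver triggers to participants with normal baseline tests, so eligible participants with a raised baseline have no numeric trigger for some AST-based events or for ALP above 2 x ULN

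*Protocol*

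**What the plan says.** Protocol Section 10.2.1 says that, once a participant is exposed, "every liver event defined in Table 16-1 should be followed up by the investigator" or site staff. It presents the table as exhaustive: "Please refer to Table 16-1 in Section 16.2 for complete definitions of liver laboratory triggers". Follow-up there means repeat liver chemistry, close observation if the rise is confirmed, and a causality assessment. Tables 16-2 and 16-3 are cited for further action detail. Section 9.1.1 also points to Section 16.2 for liver results that require stopping treatment.

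Table 16-1 has one trigger list, headed "If ALT, AST and total bilirubin normal at baseline". It includes ALT or AST above 5 x ULN, ALP above 2 x ULN, bilirubin above 3 x ULN, ALT or AST above 3 x ULN with INR above 1.5, and "Potential Hy's Law cases (defined as ALT or AST" above 3 x ULN with bilirubin above 2 x ULN and no marked ALP rise). No list is given for participants whose baseline is not normal.

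Section 5.2, exclusion 21, bars "ALT) levels of more than 1.5 x upper limit of normal (ULN") at screening, with the same limit for AST. No criterion limits bilirubin.

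Table 16-2 has no baseline condition. Its title begins "Follow up requirements for liver laboratory triggers: ALT, AST and" and ends with bilirubin, yet all five enzyme rows name ALT only and there is no ALP row. The first three rows also require "TBL normal, or no change for participants with Gilbert's syndrome". The criteria printed after Table 16-2 cover isolated bilirubin rises and adverse events suggesting liver toxicity.

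**The concern.** A conditional heading implies a counterpart for participants who do not meet the condition, and none is present. Followed as written, the condition removes numeric triggers from eligible participants, and the action table restores only part of them because it is written around ALT.

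The most serious instance is the AST form of the protocol's own potential Hy's Law case. The ALT form requires interruption under Table 16-2. The AST form, in a participant with a raised baseline test, has no row.

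Timing is also at stake. Table 16-2 asks for a full panel within 48 to 72 hours. Without a trigger, the next scheduled chemistry may be up to 84 days away (Week 40 to Week 52, Day 281 to Day 365: 365 - 281 = 84). Safety is the primary objective of this study.

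**Working it through.** No sample size or error rate is involved. The check matches each purely laboratory trigger in Table 16-1 against the rows that remain when the baseline condition is not met.

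**Inputs.** Table 16-1 triggers, counting ALT and AST separately (8 in all); Table 16-2 rows; the criteria printed after Table 16-2. All values except INR are multiples of ULN.

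**Conventions.** The participant is asymptomatic and does not have Gilbert's syndrome. A bilirubin rise counts as isolated when ALT and AST are both at or below 3.

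| Table 16-1 trigger | Row available without the baseline condition | Match |
|---|---|---|
| ALT >3 with INR >1.5 | combined ALT row | full |
| ALT >3 with bilirubin >2 | combined ALT row | full |
| Bilirubin >3 | isolated rows, or combined row if ALT >3; none if AST >3 with ALT <=3 | partial |
| ALT >5 | first three rows if bilirubin normal; combined row if bilirubin >2 or INR >1.5; none if bilirubin >1-2 and INR <=1.5 | partial |
| AST >5, ALT <=3 | none | none |
| AST >3 with INR >1.5, ALT <=3 | none | none |
| AST >3 with bilirubin >2, ALT <=3 | none | none |
| ALP >2 | none | none |

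Tally: 2 full + 2 partial + 4 none = 8. The missed part of the bilirubin trigger adds no new case: it falls within the AST-with-bilirubin row or, if ALP exceeds 2, within the ALP row.

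**Effect of the table's layout.** In the table text, the trigger for ALT or AST above 5 stands just before the baseline heading. If it is unconditional, the ALT >5 and AST >5 lines are covered and drop out, leaving 2 full + 1 partial + 3 none = 6. The three unmatched triggers (AST with INR, AST with bilirubin, ALP) remain under either reading.

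**Worked profiles** (raised baseline; unstated enzymes at or near ULN, INR 1 unless given):

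- ALT 4, bilirubin 2.5: combined row applies, interrupt.
- Same values with the enzymes swapped (AST 4, ALT 1.2, bilirubin 2.5): no row under either reading. If the isolated-bilirubin row for >1.5 to 3.0 were used anyway, dosing would continue.
- ALP 4: no row.
- AST 10 alone: no row if the heading governs the first trigger.
- ALT 10, bilirubin 1.3: no row under that same reading. A row does apply if INR is 1.6, if liver symptoms are present, or if the bilirubin is an unchanged Gilbert's value.
- ALT 10, bilirubin 0.8: the ALT rows apply, so there is no gap.

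With a normal baseline, Table 16-1 catches every one of these profiles.

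**The case against.** The strongest reply is that the protocol does not leave these participants unwatched. Table 8-1 schedules chemistry at every visit. Under Section 16.1 the central laboratory flags out-of-range values on a report that the investigator reviews and signs. Section 10.1.1 requires clinically significant results to be identified by looking at values outside range and at changes from baseline. The row for adverse events suggesting liver toxicity has no baseline condition and requires causality to be established. Section 9.1.1 covers other laboratory abnormalities that in the investigator's judgement prevent continuing. Exclusion 21 also removes anyone with past or current hepatic disease.

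All of this stands and makes the gap smaller. It does not close it. Each route turns on the investigator judging the value significant, interruption is then only to be considered, and follow-up is discretionary. Sections 10.1.1 and 16.1 send the investigator back to Section 16.2 for alert values, where the only numeric AST and ALP thresholds are those in Table 16-1.

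A second reply is that the heading cannot be meant literally, since it would also make clinical jaundice a liver event only when baseline was normal. That is a fair point about intent, and a reason to correct the wording.

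A reader might infer more than the documents support:

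- **That raised-baseline participants have no liver rules.** They do: Table 16-2 applies to them and covers most ALT rises.
- **That every ALT rise above 5 x ULN with bilirubin of 1 to 2 x ULN is uncovered.** It is uncovered only without symptoms, with INR at or below 1.5 and without unchanged Gilbert's bilirubin, and only if the heading governs the first trigger.
- **That the analysis is affected.** SAP Table 2-9 uses ALT or AST, ALP and the potential Hy's Law criterion without requiring a normal baseline.

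**Conclusion.** The point holds in a limited form. Under either reading of the layout, three numeric triggers are missing for asymptomatic participants with a raised baseline ALT, AST or bilirubin: AST above 3 x ULN with INR above 1.5 (ALT at or below 3 x ULN), AST above 3 x ULN with bilirubin above 2 x ULN (ALT at or below 3 x ULN), and ALP above 2 x ULN. If the heading also governs the first trigger, AST above 5 x ULN alone and the narrowly defined ALT-with-bilirubin case join them.

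This rests on Table 16-1 having no list for abnormal baselines, and on reading isolated bilirubin as excluding a concurrent transaminase rise above 3 x ULN. The documents do not give the share of the roughly 70 participants with a raised baseline test or the rate of these events, so no count of those affected can be derived. Few are likely, and nothing here shows that harm is probable. Severity is minor. The change is worth making because a stated condition takes safety triggers away from eligible participants.

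**What to change.** 1. In Table 16-1, delete the normal-baseline condition, or state that the ULN-based triggers apply whatever the baseline ALT, AST or bilirubin, keeping the Gilbert's exception. This alone brings all the cases above under Section 10.2.1.
2. In Table 16-2, replace ALT with ALT or AST in the five enzyme rows so that they match the table's title.

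Do not extend the first Table 16-2 row to bilirubin above ULN. Its instruction is to keep dosing, and that should not attach to a combined ALT and bilirubin rise.

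The cost is a wording change in Appendix 2, with an occasional unscheduled chemistry sample (already provided for in Table 8-1) or treatment interruption. The second change also gives action rows to normal-baseline participants with AST-only rises. Eligibility, scheduled visits and the SAP are unchanged.

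### For asymptomatic high ALT, Table 16-2 mandates interruption at normal bilirubin and above 2 × ULN, but not in between

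*Protocol*

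**What the plan says.** Protocol Section 16.2 (Appendix 2), Table 16-2, sets the action by ALT, bilirubin and liver symptoms. It has five ALT rows, lettered here for reference:

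- **A**, no symptoms: "ALT > 3 ULN TBL normal, or no change for participants with Gilbert's syndrome". Continue dosing.
- **B**, no symptoms: "ALT > 5 x ULN for more than two weeks TBL normal, or no change for participants with Gilbert's syndrome". Interrupt.
- **C**, no symptoms: "ALT > 8 x ULN TBL normal, or no change for participants with Gilbert's syndrome". Interrupt.
- **D**, no symptoms: "ALT > 3 x ULN TBL > 2 x ULN (or INR > 1.5"; for participants with Gilbert's syndrome the criterion is given as "Gilbert's syndrome: Doubling of direct bilirubin". Interrupt.
- **E**, liver symptoms present: ALT above 3 × ULN at any bilirubin. Interrupt.

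Rows B to E share one restart condition: "Study drug can be restarted only if another etiology is identified and liver enzymes return to baseline". The bilirubin rows further down are headed as isolated elevations; at above 1.5 to 3.0 × ULN they continue dosing.

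Table 16-1 lists ALT or AST above 5 × ULN as a liver trigger, under the heading "If ALT, AST and total bilirubin normal at baseline". For a confirmed elevation, Section 10.2.1 calls for close observation, "including consideration of treatment interruption if deemed appropriate".

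**The concern.** Rows B and C stop applying once bilirubin rises above normal, and row D does not start until it exceeds 2 × ULN. In between, at an ALT that is already an interruption limit on its own, the table gives no ALT instruction. The rule therefore weakens as bilirubin first rises, which is the wrong direction for a liver stopping rule, and no rationale is given.

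What is lost in that band is the mandatory interruption, the strict restart condition, and the table's timed repeat panel (48 to 72 hours) and workup. An investigator could keep dosing, or could interrupt under Section 6.6, which allows restart at the next scheduled visit once the safety risk has resolved. Sites could handle the same laboratory picture differently. Safety is the primary objective of this study, and Section 4.5 names drug discontinuation rules among its risk mitigations.

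**Working it through.** The plan states no figure on this point, so the check is one of coverage: which rows does each participant meet?

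**Inputs.** Rows A to E as listed. Assumption: normal TBL means at most 1 × ULN, since the protocol does not define it. Participant: no liver symptoms, INR at most 1.5.

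**Step 1. Apply the rows** at both ALT limits and six bilirubin states.

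| Bilirubin state | ALT 6 × ULN, more than two weeks | ALT 9 × ULN |
|---|---|---|
| No Gilbert's, TBL 1.0 × ULN | B: interrupt (A also met) | C: interrupt (A also met) |
| No Gilbert's, TBL 1.5 × ULN | no ALT row | no ALT row |
| No Gilbert's, TBL 2.5 × ULN | D: interrupt | D: interrupt |
| Gilbert's, TBL unchanged | B: interrupt (A also met) | C: interrupt (A also met) |
| Gilbert's, TBL changed, direct bilirubin not doubled | no ALT row | no ALT row |
| Gilbert's, direct bilirubin doubled | D: interrupt | D: interrupt |

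Total: 2 × 6 = 12 combinations. Interruption required: 4 states × 2 = 8. No ALT row: 2 states × 2 = 4.

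**Step 2. Locate the edges** without Gilbert's syndrome. TBL of 1.1, 1.5, 1.6 and 2.0 × ULN matches no ALT row at ALT 6 × ULN for 15 days or at ALT 9, 15 or 25 × ULN. TBL of 1.0 matches B or C, and TBL of 2.1 matches D. The gap is TBL above 1 and up to 2 × ULN.

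**Step 3. Test the qualifiers** at ALT 9 × ULN and TBL 1.5 × ULN. INR 1.6 brings in row D, liver symptoms bring in row E, and unchanged TBL in Gilbert's syndrome brings in row C. All three interrupt, so the gap needs every qualifier: asymptomatic, INR at most 1.5, and no Gilbert's syndrome or the parallel Gilbert state.

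**Step 4. Compare repairs to rows B and C.** With a limit of TBL at most 2 × ULN, and the Gilbert clause kept and governing those participants: 8 + 2 = 10 of 12 require interruption. With *regardless of TBL*: 10 + 2 = 12 of 12.

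**Step 5. Check overlap.** Row A has no upper ALT limit. In 4 of the 12 combinations (normal or unchanged TBL) it is met together with an interrupt row, under all three wordings.

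**The case against.** Four arguments have weight.

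- **Other safeguards cover this participant.** ALT above 5 × ULN is a Table 16-1 trigger. Section 10.2.1 then calls for repeat chemistry, close observation and causality assessment, and lists serology, imaging and hepatologist consultation at the investigator's discretion. A clinically significant laboratory value is an adverse event under Section 10.1.1, so the Table 16-2 row on adverse events that may indicate liver toxicity would probably apply too. Section 9.1.1 requires discontinuation where continuing might be a safety risk. This stands as a limit on the harm, but each route asks only that interruption be considered, or rests on judgement, or (for liver results in Section 9.1.1) refers back to Section 16.2. None restores the threshold or the restart condition. The Table 16-1 triggers are also headed for participants with normal baseline values, while exclusion criterion 21 sets no bilirubin limit.
- **Normal might be read as at most 1.5 × ULN**, since the appendix starts bilirubin action above that level. The gap then narrows to above 1.5 and up to 2 × ULN but does not close. That reading is also less natural: row E says normal or elevated where it means to include raised values, and the SAP grades TBL from just above ULN (Table 2-8).
- **The case is rare.** It needs a marked ALT rise, no symptoms, INR at most 1.5 and bilirubin in one band. Exclusion criterion 21 also removes participants with hepatic disease or raised transaminases at screening. This stands.
- **It may be late.** The SAP's fourth amendment, dated January 2024, precedes final database lock, so little dosing may remain in this study. That affects the value of the change here, not whether the gap exists.

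**Conclusion.** The concern holds. In Table 16-2, at either ALT interruption limit, stopping is mandatory with normal TBL and with TBL above 2 × ULN, but not between the two, for an asymptomatic participant without Gilbert's syndrome whose INR is at most 1.5. Four of 12 combinations fall outside every ALT row, two of them in Gilbert's syndrome.

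The result rests on two readings. Normal TBL is taken as at most 1 × ULN; at 1.5 × ULN the gap is narrower but remains. In Gilbert's syndrome, doubling of direct bilirubin is taken to replace the TBL limit in row D; if both apply, the Gilbert gap is confined to TBL at most 2 × ULN.

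The documents give no rate for such elevations, so the counts describe the rule and not the risk. A participant already interrupted at normal TBL stays under the restart condition and is unaffected. This is a narrow participant-safety gap that should be closed. Monitoring continues in the band, and no planned analysis changes.

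**What to change.** In rows B and C, replace the bilirubin condition, including its Gilbert clause, with *regardless of TBL*. This is better than a limit of 2 × ULN because it also closes the Gilbert gap. Add one sentence stating that the stricter action governs when a participant meets more than one row, which settles the overlap with row A.

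One residue remains: ALT above 3 × ULN but below the two limits, with TBL above 1 and up to 2 × ULN, still matches no ALT row and rests on Section 10.2.1 and investigator judgement. At normal TBL the same ALT values continue dosing.

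The cost is two table cells and one sentence, plus an occasional extra interruption. No scheduled visits or assessments are added. Section 14.1 requires a written amendment with IRB/IEC approval before implementation, so it is best bundled with the next one. If dosing here is complete, correct the table before it is reused in the extension protocol under consideration.
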